Type 1 diabetes mellitus (T1DM) or Hyperglycemia	New onset T1DM or Grade 3 or 4 hyperglycemia associated with evidence of β -cell failure	Withhold	
 Initiate insulin replacement therapy for subjects with T1DM Administer anti-hyperglycemic in subjects with hyperglycemia 	
 Monitor subjects for hyperglycemia or other signs and symptoms of diabetes.
Hypophysitis	Grade 2	Withhold	
 Administer corticosteroids and initiate hormonal replacements as clinically indicated. 	
 Monitor for signs and symptoms of hypophysitis (including hypopituitarism and adrenal insufficiency)
	Grade 3 or 4	Withhold or permanently discontinue ¹		
Hyperthyroidism	Grade 2	Continue	
 Treat with non-selective beta-blockers (e.g. propranolol) or thionamides as appropriate 	
 Monitor for signs and symptoms of thyroid disorders.
	Grade 3 or 4	Withhold or Permanently discontinue ¹		
Hypothyroidism	Grade 2-4	Continue	
 Initiate thyroid replacement hormones (e.g. levothyroxine or liothyronine) per standard of care 	
 Monitor for signs and symptoms of thyroid disorders.

Immune-related AEs	Toxicity grade or conditions (CTCAEv4.0)	Action taken to GSK3174998 ± pembrolizumab	irAE management with corticosteroid and/or other therapies	Monitor and follow-up
Nephritis and renal dysfunction	Grade 2	Withhold	
 Administer corticosteroids (methylprednisolone 1-2mg/kg or equivalent) followed by taper. 	
 Monitor changes of renal function
	Grade 3 or 4	Permanently discontinue		
Myocarditis	Grade 1 or 2	Withhold	
 Based on severity of AE administer corticosteroids 	Ensure adequate evaluation to confirm etiology and/or exclude other causes 

	Grade 3 or 4	Permanently discontinue		
All other immune-related AEs	Grade 3, or intolerable/persistent Grade 2	Withhold	
 Based on severity of AE administer corticosteroids 	
 Ensure adequate evaluation to confirm etiology or exclude other causes
	Grade 4 or recurrent Grade 3	Permanently discontinue		
NOTES:				

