7.4.1. Adverse Events and Serious Adverse Events

The definitions of an AE or SAE can be found in [Appendix 8](#).

The investigator and their designees are responsible for detecting, documenting, and reporting events that meet the definitions of an AE or SAE.

7.4.1.1. Time Period and Frequency for Collecting Adverse Events and Serious Adverse Events Information

- AEs and SAEs will be collected from the start of study treatment until the follow-up contact (see Section 7.4.1.3) at the time points specified in the Time and Events Table (Section 7.1, [Table 13](#)).
- Medical occurrences that begin prior to the start of study treatment but after obtaining informed consent may be recorded on the Medical History/Current Medical Conditions section of the eCRF.
- Any AESI and SAEs assessed as related to study participation (e.g., protocol-mandated procedures, invasive tests, or change in existing therapy) or related to a GSK product will be recorded from the time a subject consents to participate in the study up to 90 days after the last dose of study drug(s). If another anti-cancer agent is started during the 90 day reporting period, only AESI and SAEs that occur within 30 days from the last dose of study drug(s) should be recorded. SAEs must be reported within 24 hours to the Sponsor either by electronic media or paper

- All AESI and SAEs will be recorded and reported to GSK within 24 hours, as indicated in [Appendix 8](#).
- Investigators are not obligated to actively seek AEs or SAEs in former study subjects. However, if the investigator learns of any SAE, including a death, at any time after a subject has been discharged from the study, and he/she considers the event reasonably related to the study treatment or study participation, the investigator must promptly notify GSK.

NOTE: The method of recording, evaluating, and assessing causality of AEs and SAEs plus procedures for completing and transmitting SAE reports to GSK are provided in [Appendix 8](#).

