12.11. Appendix 11: Adverse Events of Special Interest

The list of terms and reporting requirements for GSK AESI are provided below. These are selected non-serious AEs and SAEs that **must be reported to GSK** regardless of relationship to study treatment. Any event that meets the criteria described below must be reported regardless of investigator-determined relationship to study treatment or if considered immune-related (unless otherwise specified). Investigators/study coordinators/designated site personnel are required to record these experiences in the eCRF (as described in the eCRF completion guidance document) and to provide supplemental information (such as medical history, concomitant medications, investigations, etc.) about the event. Please note this table lists known AESI, additional events may be identified during the course of the study.

Pneumonitis (reported as AESI if \geq Grade 2)		
Acute interstitial pneumonitis	Interstitial lung disease	Pneumonitis
Colitis (reported as AESI if \geq Grade 2 or any grade resulting in dose modification or use of systemic steroids to treat the AE)		
Intestinal Obstruction	Colitis	Colitis microscopic
Enterocolitis	Enterocolitis hemorrhagic	Gastrointestinal perforation
Necrotizing colitis	Diarrhea	
Endocrine (reported as AESI if \geq Grade 3 or \geq Grade 2 and resulting in dose modification or use of systemic steroids to treat the AE)		
Adrenal Insufficiency	Hyperthyroidism	Hypophysitis
Hypopituitarism	Hypothyroidism	Thyroid disorder
Thyroiditis	Hyperglycemia, if \geq Grade 3 and associated with ketosis or metabolic acidosis (DKA)	
Endocrine (reported as AESI)		
Type 1 diabetes mellitus (if new onset)		
Hematologic (reported as AESI if \geq Grade 3 or any grade resulting in dose modification or use of systemic steroids to treat the AE)		
Autoimmune hemolytic anemia	Aplastic anemia	Thrombotic Thrombocytopenic Purpura (TTP)
Idiopathic (or immune) Thrombocytopenia Purpura (ITP)	Disseminated Intravascular Coagulation (DIC)	Hemolytic Uremic Syndrome (HUS)
Any Grade 4 anemia regardless of underlying mechanism		
Hepatic (reported as AESI if \geq Grade 2, or any grade resulting in dose modification or use of systemic steroids to treat the AE)		
Hepatitis	Autoimmune hepatitis	Transaminase elevations (ALT and/or AST)
Infusion Reactions (reported as AESI for any grade)		
Allergic reaction	Anaphylaxis	Cytokine release syndrome
Serum sickness	Infusion reactions	Infusion-like reactions

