Neurologic (reported as AESI for any grade)		
Autoimmune neuropathy	Guillain-Barré syndrome	Demyelinating polyneuropathy
Myasthenic syndrome		
Ocular (report as AESI if \geq Grade 2 or any grade resulting in dose modification or use of systemic steroids to treat the AE)		
Uveitis	Iritis	
Renal (reported as AESI if \geq Grade 2)		
Nephritis	Nephritis autoimmune	Renal Failure
Renal failure acute	Creatinine elevations (report as AESI if \geq Grade 3 or any grade resulting in dose modification or use of systemic steroids to treat the AE)	
Skin (reported as AESI for any grade)		
Dermatitis exfoliative	Erythema multiforme	Stevens-Johnson syndrome
Toxic epidermal necrolysis		
Skin (reported as AESI if \geq Grade 3)		
Pruritus	Rash	Rash generalized
Rash maculo-papular		
Any rash considered clinically significant in the physician's judgment		
Other (reported as AESI for any grade)		
Myocarditis	Pancreatitis	Pericarditis
Any other Grade 3 event which is considered immune-related by the physician		

Pembrolizumab-specific events of clinical interest for this trial include:

- An overdose of pembrolizumab, as defined in Section 6.8.2 - Definition of an Overdose for This Protocol and Reporting of Overdose to the Sponsor, that is not associated with clinical symptoms or abnormal laboratory results.
- An elevated AST or ALT lab value that is greater than or equal to 3X the upper limit of normal and an elevated total bilirubin lab value that is greater than or equal to 2X the upper limit of normal and, at the same time, an alkaline phosphatase lab value that is less than 2X the upper limit of normal, as determined by way of protocol-specified laboratory testing or unscheduled laboratory testing.*

*Note: These criteria are based upon available regulatory guidance documents. The purpose of the criteria is to specify a threshold of abnormal hepatic tests that may require an additional evaluation for an underlying etiology.

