### 13.3. Adverse Events of Special Interest

Characteristics (e.g., number of occurrences, action taken, grade, etc.) of AESI (also referred to as immune-related adverse event, see Appendix 11 in protocol) will be summarized separately.

In addition, AESI will be listed separately.

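### Appendix 11's catch-all row for adverse events of special interest (AESI) stops at Grade 3, contradicting its own heading and, read literally, leaving unlisted Grade 4 and 5 immune-related events out of the AESI set

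*Protocol*

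**What the plan says.** Protocol Appendix 11 lists AESI terms in groups, most with a grade threshold in the group heading. Minimum grades in those headings carry an explicit sign, for example "Skin (reported as AESI if \geq Grade 3"). The last group is headed "Other (reported as AESI for any grade"). It names myocarditis, pancreatitis and pericarditis, and closes with "Any other Grade 3 event which is considered immune-related by the physician". The introduction to the appendix leaves the list open: "Please note this table lists known AESI, additional events may be identified during the course of the study".

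Protocol Section 7.4.1.1 attaches expedited reporting to the classification: "All AESI and SAEs will be recorded and reported to GSK within 24 hours". Footnote d of Table 13 sets collection at no less than 90 days after the last dose for AESIs and SAEs, against 30 days for other AEs. Section 7.4.1.3 requires SAEs and non-serious AESIs to be followed until they resolve, stabilise or are explained, or the subject is lost to follow-up.

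SAP Section 13.3 summarises "Characteristics (e.g., number of occurrences, action taken, grade, etc.) of AESI" and defines the set only by cross-reference: "also referred to as immune-related adverse event, see Appendix 11 in protocol". SAP Section 13.2 adds an AESI line in the AE overview and an AESI summary by preferred term.

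**The concern.** A catch-all exists to bring in important events that nobody thought to list. This one takes in the Grade 3 events and, on its wording, leaves out the more severe ones. The heading above it says something different, and the SAP gives a programmer no rule for choosing between them.

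Two things are at stake. The AESI displays are where a reader looks for the grade profile of immune toxicity, so losing the most severe unlisted events would make that profile look milder than it was. AESI status also carries reporting, collection and follow-up duties that an ordinary non-serious AE does not have.

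**Working it through.** No arithmetic applies to the classification itself; the check is a comparison of texts.

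**Step 1. How each reading classifies an unlisted immune-related event.**

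| Reading | Grade 1–2 | Grade 3 | Grade 4 | Grade 5 |
|---|---|---|---|---|
| Catch-all row, literal | no | AESI | no | no |
| Heading governs | AESI | AESI | AESI | AESI |
| SAP 13.3 gloss taken as the definition | AESI | AESI | AESI | AESI |
| Row read as Grade 3 or higher | no | AESI | AESI | AESI |

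The heading and the gloss agree for unlisted events. They could differ for listed terms below their threshold, which the gloss would bring in and the headings would not. Only the literal row includes a grade while excluding the grades above it.

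**Step 2. Is the bare grade deliberate?** Minimum grades in the group headings, and in the hyperglycemia and creatinine entries, carry the sign, so a sign lost from this one row is unlikely, though the page is worth a look. One other free-text entry, for Grade 4 anemia, also names a bare grade. The table's convention is therefore not uniform, and a drafting slip is the likeliest explanation.

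**Step 3. Does the protocol provide for such events?** Table 10 (Section 6.3.1.1) has a residual row for immune-related events not otherwise named, with a category of "Grade 4 or recurrent Grade 3". That shows unlisted Grade 4 events were provided for. It does not show how often they were expected.

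**Step 4. Does another passage settle the grade?** The open-list sentence has no grade rule, and neither does SAP 13.3. I found no current text that extends the row to Grades 4 and 5.

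**Step 5. What the literal row removes, and what remains.**

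| Output or duty | Unlisted immune-related Grade 4–5 event |
|---|---|
| AESI line in the AE overview (SAP 13.2) | missing |
| AESI summary by preferred term (SAP 13.2) | missing |
| AESI characteristics summary (SAP 13.3) | missing |
| AESI listing (SAP 13.3) | missing |
| On-treatment AEs by maximum grade; listing of all AEs (SAP 13.2) | present, if collected |
| SAE and fatal SAE outputs (SAP 13.2, 13.4) | present if serious; Grade 5 always is |
| Discontinuation outputs (SAP 13.2, 13.5) | present if treatment was stopped for the event |
| DLT summary (SAP 13.2) | present if recorded as a DLT |
| 24-hour report, 90-day collection, mandatory follow-up | kept if serious; lost if non-serious |

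The last line matters for non-serious Grade 4 events. Protocol Appendix 8 defines life-threatening by actual risk of death at the time, not by CTCAE grade, so a Grade 4 laboratory abnormality need not be an SAE. The longer window is relevant because Section 6.3.1.1 warns that immune-related events may appear months after dosing ends.

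**Step 6. Size and direction.** If *k* unlisted immune-related events reached Grade 4 or 5, a literal AESI flag omits all *k*. The documents do not give *k*. If it is 0, no output changes; if it is positive, the AESI displays can only look less severe.

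**Step 7. What can still be changed.** Amendment 4 states that all subjects had completed treatment by 5 November 2019. Ninety days from that date is 25 (to 30 November) + 31 (December) + 31 (January) + 3 = 3 February 2020, one day before the amendment's date of 4 February 2020. Taking the last dose as no later than 5 November, the minimum AESI window had already closed for every subject.

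**The case against.** The strongest reply is that nobody meant to exclude Grades 4 and 5. The heading says any grade, the list is expressly open, and the SAP treats AESI as another name for immune-related events. The anemia entry shows that bare grades in this table can be loose drafting. Sites recorded AESI under eCRF completion guidance that is not among these documents, so the literal rule may never have been applied. All of this is fair, and it makes intent fairly clear. It does not supply a rule: the row and its heading still give different AESI sets, and the SAP does not choose.

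A reader might infer that severity is understated in the primary safety results as a whole. The documents do not support that. The primary endpoints name AEs, SAEs, DLTs, withdrawals due to AEs, dose reductions or delays and changes in safety assessments; AESI is not among them as a category. The affected events stay in the maximum-grade summary of all AEs. Table 10 also attaches permanent discontinuation to the residual Grade 4 category, so an on-treatment event handled that way would appear in the discontinuation outputs too.

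A reader might also infer that an SAE cannot appear in the AESI table. Appendix 11 describes AESI as including both non-serious and serious events, so the two sets overlap. Only an SAE that is not also an AESI stays out.

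**Conclusion.** Wrong as written; minor. The catch-all row contradicts its heading and, followed literally, gives an AESI set that includes unlisted immune-related events at Grade 3 and excludes them at Grades 4 and 5. Four AESI outputs inherit the gap. The only events that also lose reporting, collection and follow-up duties are non-serious, unlisted Grade 4 events.

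The number of events is unknown and may be zero. The conclusion assumes that the row, not its heading, drives the flag, and that no separate eCRF or dataset specification already corrects it. The overall primary safety results are not understated on this account, apart from any non-serious event that went uncollected after day 30 because it was not treated as an AESI.

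**What to change.** In Appendix 11, reconcile the row with its heading so that it covers any other event of Grade 3 or higher that the physician considers immune-related. Keep the reference to the physician so that it stays clear who decides.

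With treatment over, the useful change is in the SAP. Section 13.3 should state, before database freeze, that unlisted immune-related events of Grade 3 or higher already in the AE database are flagged as AESI, and that the flag feeds the outputs in both 13.2 and 13.3. SAP Section 1 places final-analysis decisions before freeze, so the rule belongs there.

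The cost is one phrase in the protocol, one sentence in the SAP and a flag derivation. There are two limits. The flag needs the physician's judgement of immune-relatedness, and the documents do not show that it was recorded for events not reported as AESI, so some records may need a query. Non-serious events after day 30 that were never collected cannot be recovered by re-flagging; the study report should say so.

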12.12. Appendix 12: CKD-EPI Formula

CKD stage: Kidney Disease Outcomes Quality Initiative (KDOQI) CKD stages 3/4/5 defined by eGFR using the CKD Epidemiology Collaboration (CKD-EPI) formula [Levey, 2009].

$$\text{GFR} = 141 \times \min(S_{\text{cr}}/\kappa, 1)^{\alpha} \times \max(S_{\text{cr}}/\kappa, 1)^{-1.209} \times 0.993^{\text{Age}} \times 1.018 \text{ [if female]} \times 1.159 \text{ [if black]}$$

where:

S_{cr} is serum creatinine in mg/dL,

κ is 0.7 for females and 0.9 for males,

α is -0.329 for females and -0.411 for males,

min indicates the minimum of S_{cr}/κ or 1, and

max indicates the maximum of S_{cr}/κ or 1.

12.13. Appendix 13: Protocol Amendment Changes

12.13.1. Amendment 1

12.13.1.1. Where the Amendment Applies

This amendment applies to all sites and countries.

12.13.1.2. Summary of Amendment Changes with Rationale

Amendment 1 incorporates changes to Section 4.1.4, Dose-Limiting Toxicities; 5.4 Withdrawal/Stopping Criteria; and 6.3.1.12, Dose Delay as requested by the United States FDA.

Additionally, the SAE contact information was updated due to internal departmental changes.

12.13.1.3. List of Specific Changes

MEDICAL MONITOR/SPONSOR INFORMATION PAGE

REVISED TEXT:

Medical Monitor/Serious Adverse Event (SAE) Contact Information:

Role	Name	Office Phone Email Address	Mobile	Fax
Primary Medical Monitor	PPD [REDACTED], MD	PPD [REDACTED] [REDACTED]	PPD [REDACTED]	
Secondary Medical Monitor	PPD [REDACTED], MD, PhD	PPD [REDACTED] [REDACTED]	PPD [REDACTED]	
SAE contact information		PPD [REDACTED] [REDACTED]		PPD [REDACTED]

Section 4.1.4 Dose-Limiting Toxicity

REVISED TEXT:

Table 4 Dose-Limiting Toxicity Criteria

Toxicity	DLT Definition
Hematologic	
 • Febrile neutropenia • Grade 4 neutropenia of >7 days' duration or requiring G-CSF • Grade 4 anemia of any duration • Grade 4 thrombocytopenia of any duration or Grade 3 thrombocytopenia with bleeding
Non-hematologic	
 • Grade 4 toxicity • Grade 3 toxicity that does not downgrade to Grade 1 \leq Grade 2 or baseline within 3 days despite optimal supportive care^a, with the following exceptions: 
 • Laboratory abnormality that is not clinically significant according to the investigators (for example, isolated Grade 3 elevation of amylase or lipase not associated with clinical or radiographic evidence of pancreatitis) • Grade 3 endocrinopathy that is adequately controlled by hormonal replacement • Any Grade 2 ocular toxicity requiring systemic steroids, or any \geq Grade 3 ocular toxicity
Other	
 • Toxicity that results in permanent discontinuation of GSK3174998 or GSK3174998 and pembrolizumab during the first 4 weeks of treatment • Any other toxicity considered to be dose-limiting that occurs beyond 4 weeks will be considered in the selection of the dose for expansion cohorts • Any other event which in the judgment of the investigator and GSK Medical Monitor is considered to be a DLT

- a. Suggested management guidelines described in Section 6.3.1 for toxicity and may include systemic corticosteroids for immune-related toxicities; if use of systemic corticosteroids delays administration of the second dose of study treatment but the event does not otherwise meet the DLT criteria for non-hematologic toxicity, the dose delay will not be considered a DLT.
- b. DLT = Dose-limiting toxicity; G-CSF = Granulocyte colony-stimulating factor; AST = Aspartate aminotransferase; ALT = Alanine aminotransferase; ULN = Upper limit of normal; GSK = GlaxoSmithKline

Section 5.4 Withdrawal/Stopping Criteria

REVISED TEXT:

Subjects will receive study treatment for the scheduled time period, unless one of the following occurs earlier: disease progression (as determined by irRECIST), death, or unacceptable toxicity, including meeting stopping criteria for liver chemistry defined in Section 5.4.1. In addition, study treatment might be permanently discontinued for any of the following reasons:

- Deviation(s) from the protocol
- Request of the subject or proxy (withdrawal of consent by subject or proxy)
- Investigator's discretion

- Subject is lost to follow-up
- Study is closed or terminated
- Subjects with infusion delays greater than 3 weeks due to toxicity ~~>49 days (i.e., 2 missed doses + 7 days)~~ should discontinue study drug(s) unless the treating investigator and Sponsor/Medical Monitor agree there is strong evidence supporting continued treatment.

Note: Subjects who require permanent discontinuation of one of the study treatments due to toxicity in a given treatment combination must permanently discontinue both treatments (unless continued treatment with the remaining agent is agreed upon by the treating investigator and Sponsor/Medical Monitor) in that combination and the reason for discontinuation must be recorded. The treatment discontinuation visit (TDV) should be conducted within 30 days of the decision to discontinue study drug(s).

- Intercurrent illness that prevents further administration of study treatment(s)
- Criteria for discontinuation of study drug(s) as described in Section 6.3.1 (Safety Management Guidelines) have been met
- Criteria described in Section 5.4.2 (QTcF Stopping Criteria) have been met
- Criteria described in Section 5.4.3 (Stopping Rules for Clinical Deterioration) have been met

Section 6.3.1.12 Dose Delay

REVISED TEXT:

If there is a dose delay between 1 and 7 days, the procedures at the original scheduled visit (including dosing) should be performed as soon as possible. If the delay is ≥ 8 days, the visit and dose(s) will be considered missed. The procedures at the next scheduled visit should be performed, and subsequent visits will follow Q3W. Subjects with infusion delays greater than 3 weeks due to toxicity ~~>49 days (i.e., 2 missed doses + 7 days)~~ should discontinue study drug(s) unless the treating investigator and Sponsor/Medical Monitor agree there is strong evidence supporting continued treatment. For subjects requiring elective surgery or radiation therapy, every effort should be made to wait 1 to 2 weeks after the last dose of study drug(s) before performing surgery or starting radiation. Study drug(s) should not be administered again until 1 to 2 weeks after recovery from surgery or radiation (see Section 6.10.1. for details on permitted medications and non-drug therapies).

12.13.2. Amendment 2 Protocol Changes for Amendment 2 (16-AUG-2016) from the Protocol Amendment 1 (17-AUG-2015)

Where the Amendment Applies

This amendment applies to all sites and countries.

Summary of Amendment Changes with Rationale

Amendment 2 includes the addition of preliminary clinical data to support the initiation of Part 2/combo with pembrolizumab, the addition of a new Pharmacodynamic Cohort to allow collection of additional tumor biopsies, removal of Soft Tissue Sarcoma from the targeted tumor types, extension of GSK3174998 dosing up to 2 years or 35 cycles, definitions of analyses for anticancer activity, addition and clarifications of procedures in the T&E table, clarification on the use of CRM for dose escalation, as well as minor typographical and/or inconsistent language throughout the protocol.

List of Specific Changes

Section 1 PROTOCOL SYNOPSIS FOR STUDY 201212 (ENGAGE-1)

REVISED TEXT:

Objectives/Endpoints:

The primary objectives of the study are to evaluate the safety and tolerability and to identify the maximum tolerated dose (MTD) or maximum administered dose (MAD) of GSK3174998 when administered intravenously as monotherapy (Part 1) or in combination with pembrolizumab (Part 2) to subjects with selected advanced or recurrent solid tumors. Secondary objectives include: the evaluation of antitumor activity; characterization of pharmacokinetics (PK) for GSK3174998 when administered alone; characterization of PK for GSK3174998 and pembrolizumab when administered in combination; ~~evaluation of pharmacodynamic activity in the blood and tumor microenvironment~~; and determination of the immunogenicity of GSK3174998 when administered alone or for GSK3174998 and pembrolizumab when administered in combination. Exploratory objectives include evaluation of pharmacodynamic activity in the blood and tumor microenvironment.

2nd point:

Antitumor activity endpoints: Objective response rate (ORR) and Disease Control Rate (DCR) (complete response [CR]+partial response [PR]+stable disease [SD] \geq 12 weeks), time to response (TTR), duration of response (DOR), progression-free survival (PFS), and overall survival (OS). Unless otherwise specified, all response endpoints will be assessed by Response Evaluation Criteria in Solid Tumors (RECIST) v1.1 and by irRECIST (immune-related RECIST); the primary endpoint analysis will use irRECIST.

3rd point:

Pharmacodynamic endpoints: Assessment of lymphocyte OX40 receptor membrane expression and occupancy by GSK3174998, along with the phenotype, quantity, and activation state of T cells in the periphery, expression of circulating soluble factors, and changes in genomic DNA and gene expression. Assessment of tumor biopsies via immunohistochemistry (IHC) for the numbers of tumor-infiltrating lymphocytes and other immune cells expressing key phenotypic markers.

Treatment Arms and Duration:

The study includes a screening period, a treatment period, and a follow-up period. Subjects will be screened for eligibility beginning approximately 4 weeks before the start of treatment. The maximum duration of treatment with GSK3174998 ~~will be 48 weeks; the maximum duration of treatment with \pm pembrolizumab will be 2 years or 35 cycles, whichever comes first~~. The follow-up period for safety assessments will be a minimum of 3 months from the date of the last dose. The post-treatment follow-up period includes disease assessments every 12 weeks until confirmed disease progression (PD). Following PD, subjects will be contacted every 3 months to assess survival status.

In Part 1, dose escalation for GSK3174998 monotherapy will begin with a starting dose of 0.003 mg/kg GSK3174998 administered once every 3 weeks (Q3W). In Part 2, dose escalation for GSK3174998 + pembrolizumab combination therapy will begin with a fixed dose of 200 mg pembrolizumab administered Q3W and a starting dose of 0.003 mg/kg GSK3174998 ~~that is two dose levels below a tolerated dose of GSK3174998 monotherapy that has also demonstrated pharmacodynamic activity in Part 1A of the study~~. Dose adjustments are allowed to address tolerability and safety issues.

Type and Number of Subjects:

The study will enroll up to approximately 264 ~~180~~ subjects with tumor types that may include NSCLC, squamous cell carcinoma of the head and neck (SCCHN), renal cell carcinoma (RCC), melanoma, bladder cancer, ~~soft-tissue sarcoma (STS)~~, triple-negative breast cancer (TNBC), and colorectal carcinoma displaying microsatellite instability (MSI CRC).

Section 2.3.1 Background

REVISED TEXT:

An overview of the nonclinical studies of GSK3174998 and preliminary clinical data from Protocol 201212 (ENGAGE-1) ~~are~~ is provided below. Detailed information concerning the biology, pharmacology, PK, and safety can be found in the Investigators' Brochure (IB) [GlaxoSmithKline Document Number 2014N212091_00.

ADDED SECTIONS:

Section 2.3.5 Preliminary Clinical Data for GSK3174998

Data are summarized for the ongoing first time in human study with a clinical data cut-off of 17 May 2016. Data are reported for six subjects enrolled at the following GSK3174998 dose levels: 0.003 mg/kg (Cohort 1, n=1), 0.01 mg/kg (Cohort 2, n=1), and 0.03 mg/kg (Cohort 3, n=4). At the time of reporting, three subjects had discontinued treatment due to disease progression (one at each dose level).

